The study will then progress to phase 2 if the study steering committee judges that: the intervention materials have been culturally optimised for English schools while staying true to the original interventions and their theories of change; fidelity and acceptability metrics have been developed which will inform the evaluation methods and progression criteria for the pilot RCT; all other evaluation methods for the pilot RCT have been finalised; and all of the above have been appropriately informed by PPIE.

Phase 2: Pilot cluster RCT

Design overview

The pilot cluster RCT will occur in six secondary schools (four intervention, two control). Recruitment, baseline surveys of students and teachers, and randomisation will occur in March-July 2025. Schools will be randomly allocated 2:1 (1:1 in any future phase III RCT) to intervention/control stratified by free school meals (plus single/mixed sex school in phase III) in June/July 2025.(13, 14) A 2:1 allocation will allow us to pilot randomisation while ensuring diversity across four schools for intervention piloting. The intervention will be implemented in the four intervention schools from September 2025 to July 2026 accompanied by integral process evaluation and economic evaluation feasibility study (figure 1). Follow-up surveys will occur in May-July 2026. The primary outcome for the pilot RCT will be assessing criteria for progression to a phase III RCT. Indicative primary and secondary outcome measures (described below) for a phase III RCT will be assessed for completion and reliability but intervention effects on these outcomes will not be assessed. A future phase III RCT would involve 1:1 allocation to intervention and control, and 12- and 24-month follow-up.

Settings/context

The Belonging intervention is intended to be deliverable in all English secondary schools (including faith schools, free schools, academies and private schools) excluding pupil referral units and schools exclusively for SEND students. A future phase III RCT would be national in scope and include a representative sample of schools. The pilot will recruit schools in southeast England, appropriate to reduce travel time and costs. Pilot schools will be purposively recruited to vary by free-school-meals entitlement (poverty), Ofsted rating (school capacity), urban/peri-urban and ethnic make-up so that we can pilot the intervention across factors potentially affecting feasibility, reach and acceptability.(54)

Study population

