The study population is defined as students in year 8 (aged 12-13 years) at baseline (so in year 9 for intervention) plus all teachers. All student-reported measures are suitable for students in this age-group (see outcome measures below). The research will be inclusive, including of SEND students. No students deemed competent by teachers to complete data collection will be excluded from recruitment unless they do not consent to, or their parents withdraw them from, the research. Those who have mild learning disabilities or limited English will be supported to complete the questionnaire by researchers.

Analytical sample and sample size

The pilot focuses on resolving uncertainties before a phase III RCT rather than estimating effects, with no power calculation. The sample will involve approximately 140 students and 60 teachers per school (840 and 360 overall). The pilot RCT aims to include sufficient diversity of schools in terms of free school meals, Ofsted rating, urban/peri-urban location and ethnic make-up to allow piloting of the feasibility and acceptability of the intervention in diverse contexts. We judge six schools in total and four in the intervention arm is sufficient

for this because what we seek is overall diversity for the above factors rather than a school with every combination of the factors.

For the phase III RCT to detect a standardised effect of 0.2 SDs on our primary outcome, the Strengths and Difficulties Questionnaire (SDQ), at 90% power and 5% significance will require 16 schools per arm assuming 140 year-9 students surveyed per school, drop-out of 1 school per arm and an intra-cluster correlation coefficient (ICC) of 0.02. Our effect size has previously been defined as of policy significance.(55) We conservatively focus on SDQ in this calculation because its ICC is larger than that of our other primary outcome. Our estimate for the ICC for SDQ is conservative compared to estimates from recent UK research.(55) Our pilot will assess our estimates while acknowledging small-sample limitations. Our pilot will not assess preliminary intervention effects since it is not powered to do so.

Recruitment and random allocation

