We will recruit secondary schools in south-east England (all England in phase III) of all types except those exclusively for SEND students and pupil referral units. Schools in the pilot will vary by free-school-meals entitlement (poverty), Ofsted rating (school capacity), urban/periurban location and ethnic make-up so that we can pilot across factors likely to affect feasibility, reach and acceptability.(54) As with our previous trials, schools will be recruited by a combination of emails and then phone calls to schools, local authorities, school networks and academy chains. Response rates will be recorded, as will any stated reasons for non-participation.

As explained above, after baselines, schools will be randomly allocated 2:1 to intervention and control (1:1 in phase III RCT) by LSHTM clinical trials unit (CTU), stratified by free school meals (plus single/mixed sex school in phase III).(13, 14) A 2:1 allocation in the pilot RCT will enable us to pilot randomisation while ensuring sufficient diversity of schools in the intervention arm for intervention piloting. Schools will be given unique study numbers to preserve allocation concealment within the CTU. The CTU will pass on allocations to the fieldwork team who will then inform schools. Informed by the Positive Choices and 'If I Were Jack' RCTs,(56, 57) we will facilitate recruitment and retention by offering a £500 payment to all schools. Previous studies suggest that payment is now essential for maintaining school participation in research(56, 57) particularly in the post-pandemic context. Each school will be allocated a named research liaison contact to facilitate retention.

Planned intervention and comparator

The Belonging intervention combines the US Student Belonging intervention and the Teacher Empathetic Discipline intervention (see 'Review of existing evidence' above) culturally optimised for English secondary schools but retaining original procedures and theories of change. Our logic model (figure 2) integrates these original theories of change for presentation purposes to show how they work together (figure 2). The intervention is described below using the Template for Intervention Description and Replication (TIDieR) framework.(58)

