Comparator will be treatment as usual with schools continuing with existing activities to promote student mental health and prevent violence and bullying. Process evaluation will describe this. PPIE suggests that no UK schools currently use interventions resembling those proposed.

Outcome measures

Pilot outcomes

For this pilot trial, the primary outcome is assessment of criteria for progression to phase III RCT as follows:

- randomisation occurs and 5+ schools continue;
- interventions achieve 70+% fidelity and reach;
- interventions acceptable to 70+% of students and teachers;
- student survey response rates are 80+% in 5+ schools; and
- informed by qualitative research, hypotheses developed about how contextual factors affect intervention implementation and mechanisms.

The precise metrics used to assess implementation fidelity and acceptability will be defined in phase one when intervention materials are optimised. These criteria will be shared with the study steering committee and NIHR for approval. The study steering committee will judge at the end of the study whether criteria for progression to phase III RCT have been met.

Trial outcomes to be piloted

All will be measured at 12-month follow-up (24 in phase III RCT). The co-primary outcomes for a phase III RCT (assessed for performance in the pilot) are student-reported SDQ(60) and Short Warwick Edinburgh wellbeing (SWEMWBS).(61)

Student-reported secondary outcomes at 24 months are:

- aggression (Edinburgh Study of Youth Transitions and Crime school misbehaviour subscale;(62)
- bullying victimisation and perpetration in past 2 months (Revised Olweus Bully/Victim Questionnaire).(63) and
- substance use (tobacco, alcohol and drug use assessed using existing measure(64)).

Other secondary outcomes are:

- student exclusions and attendance (routine data)
- teacher-reported perceived behaviour of students (Pupil Behaviour Questionnaire(65));
- teacher-reported self-efficacy (Teacher Sense of Efficacy scale(66)); and
- teacher-reported burnout (Maslach Burnout Inventory).(67)

Secondary outcomes will also include the Child Health Utility (CHU)9D measure(68) which will be used for cost-utility analyses (see below). The CHU-9D is a validated age-appropriate measure explicitly developed using children's input.(69)

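### The 2:1 allocation makes a diverse intervention arm more likely, but ensures nothing on Ofsted rating, location or ethnic make-up, because the pilot stratifies by free school meals only

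*Protocol*

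**What the plan says.** The pilot has six schools, four intervention and two control. Under Settings/context they are to be "purposively recruited to vary by free-school-meals entitlement (poverty), Ofsted rating (school capacity), urban/peri-urban and ethnic make-up". Under Analytical sample and sample size, the same four factors justify having six schools with four in the intervention arm, with the qualification that "what we seek is overall diversity for the above factors rather than a school with every combination of the factors".

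The allocation rule, under Design overview, is: "Schools will be randomly allocated 2:1 (1:1 in any future phase III RCT) to intervention/control stratified by free school meals". Single/mixed-sex status is added only in phase III. The ratio is justified twice by diversity in the intervention arm. Design overview says: "A 2:1 allocation will allow us to pilot randomisation while ensuring diversity across four schools for intervention piloting". Recruitment and random allocation makes the same claim, with the qualifier *sufficient*: "ensuring sufficient diversity of schools in the intervention arm for intervention piloting".

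The Protocol sets no minimum number of schools per level, does not restrict the allocation on Ofsted rating, location or ethnic make-up, and plans no check of the arms for diversity. In the process evaluation section on fidelity, reach, engagement and acceptability, student exposure, uptake, engagement and acceptability are to be examined by Ofsted rating and free-school-meals entitlement, among other characteristics.

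**The concern.** Purposive recruitment makes the six schools diverse. It does not make the four intervention schools diverse, because chance decides which two become controls. Stratifying by free school meals carries that factor into both arms but does nothing directly for the other three. The stratifiers are stated outright, so this is not a detail left to a later document.

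The intervention can be observed only in the four schools that receive it. If every school at one Ofsted level becomes a control, the pilot has no fidelity, reach or acceptability data at that level. The breakdown by Ofsted rating then lacks that level, and cannot be made at all if the rating is treated as two groups. Both optimisation schools in Phase 1 are chosen to have high Ofsted ratings. If the lower-rated pilot schools were the ones lost, neither phase would test delivery in such a school.

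**Working it through.** **Inputs from the Protocol.** Six schools; 2:1 allocation; stratified by free school meals only; three further selection factors.

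**The stated split reproduces.** 6 × 2/3 = 4 intervention and 6 × 1/3 = 2 control.

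**Assumptions, because the Protocol gives no figure.** Two free-school-meals strata of three schools, one control drawn from each, giving 3 × 3 = 9 equally likely allocations. Each other factor has a less common level held by 1, 2 or 3 of the six schools. A level is lost when every school holding it becomes a control.

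**One level**

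| Schools at the level | 1:1, unstratified (20 allocations) | 2:1, unstratified (15) | 2:1, 3:3 strata (9) |
|---|---|---|---|
| 1 | 10/20 = 50% | 5/15 = 33% | 3/9 = 33% |
| 2 | 4/20 = 20% | 1/15 = 6.7% | 1/9 = 11% in different strata; 0 in the same stratum |
| 3 or more | 1/20 = 5% for three; 0 for four or more | 0 | 0 |

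With strata of two and four schools and one control from each (2 × 4 = 8 allocations), a single school is a control with probability 1/2 or 1/4 according to its stratum. A pair in different strata is lost with probability 1/8 = 12.5%.

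**At least one of three levels lost (Ofsted rating, location, ethnic make-up), 3:3 strata**

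- One school per level: from 33% (the same school holds all three) to 100% (three different schools fill one stratum, so one of them is always the control). The mean over all placements is 1 − (2/3)³ = 70%.
- Two schools per level: from 0% (every pair within one stratum) to 3/9 = 33% (three different cross-stratum pairs). The mean is 1 − (14/15)³ = 19%.
- Three schools per level: 0%.

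The means treat every placement of the levels as equally likely. The ranges do not depend on that.

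**What a restriction would leave.** With two schools per level, each different cross-stratum pair rules out one allocation, so 9 − 3 = 6 to 9 − 0 = 9 of the 9 remain. If all three pairs share one school, the three excluded allocations are exactly those in which that school is a control, so it would have no chance of control. Dropping one constraint leaves 7 allocations, and that school is a control in 1 of them. With one school per level, restriction leaves 0 to 6 of 9, and any such school would go to intervention with certainty.

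**The case against.** The sentence explains why the pilot uses 2:1 when phase III would use 1:1. Read that way the reasoning is sound: four intervention schools lose a level less often than three, as the table shows. The Protocol seeks overall and sufficient diversity, and four schools can be diverse overall with one level absent. If purposive recruitment puts three schools at each level, the risk is zero with nothing changed. Neither Ofsted rating nor ethnic make-up is defined as having two levels, and random placement sits poorly with purposive selection. The section on implementation processes also admits that assessments across schools are limited by the size of the pilot.

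Most of this stands, and it limits the point. A reader might infer that every level of every factor was promised in the intervention arm; the qualified wording does not say so. A reader might infer that the 70% fidelity, reach and acceptability criteria would be judged only in easier schools, but a lone high-rated school is as likely to be lost as a lone low-rated one. A reader might also infer that the fifth progression criterion could not be met. It asks only for "informed by qualitative research, hypotheses developed about how contextual factors affect intervention implementation and mechanisms", and does not require all four factors to be covered.

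What the objection does not answer is the word *ensuring*. A lower risk is not an assurance, and nothing in the Protocol requires three schools per level.

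**Conclusion.** The point holds as a mismatch between a stated assurance and the allocation rule. Beyond free school meals, 2:1 improves the chance of diversity in the intervention arm and guarantees none. Under 3:3 strata, a single level is lost with probability 1/3 if one school holds it, 1/9 if two schools in different strata hold it, and 0 if two in the same stratum or three or more hold it. The joint figures (33–100% with one school per level, 0–33% with two, 0 with three) depend on assumed stratum sizes and school profiles, so the 70% and 19% means should not be read as the trial's actual risk.

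A reader might take this as a flaw that undermines the pilot. The documents do not support that: no effects are to be assessed, the target is overall diversity, and the chosen ratio already reduces the risk. The practical consequence is narrower: the planned breakdown by Ofsted rating could fail, and the text claims more than the design delivers. Severity is minor.

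**What to change.** Keep the free-school-meals stratification and the 4:2 totals. Once the six schools are known, have the clinical trials unit list the possible allocations and exclude those that put every school at a level of Ofsted rating, location or ethnic make-up into control. Then draw at random from the rest, with two limits set in advance:

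- Apply the exclusion only to levels held by two or more schools. For a level held by one school, leave allocation random and state that its presence in the intervention arm is not assured. Forcing that school into intervention would conflict with piloting randomisation and with head teachers' consent to random allocation.
- Apply it only while every school keeps a non-zero chance of either arm. If constraints must be dropped, keep Ofsted rating longest, because it is the only one of the three for which a school-level breakdown is planned.

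Whether or not the restriction is adopted, replace *ensuring* in Design overview and in Recruitment and random allocation with wording that names the factors the allocation protects. If nothing else changes, that is free school meals alone.

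The cost is a short piece of allocation code and a sentence in each section, with no extra schools or data. The downside is fewer possible allocations (6 to 9 of 9 with two schools per level) and allocation probabilities that may differ between schools. Both matter little in a pilot that does not assess effects.
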